#### Safety Monitoring Committee (SMC)

The SMC will be composed of the principal investigators of each participating center, the pharmacokinetics (PK) specialist, the medical and safety representatives of the Sponsor and an independent expert in oncology/hematology phase I development. All decisions taken by the SMC and their rationale will be recorded in meeting minutes that will be integrated in the final clinical study report.

### Definition of dose limiting toxicities (DLTs)

The DLTs are identical to the events leading to treatment interruption and dose adjustment (see dose & schedule adaptation), as well as any other unforeseen drug-related AE resulting in study drug discontinuation or interruption with/without dose reduction. But only such AEs occurring during cycle 1 (or the first 21 days following the first dosing of OTX015/MK-8628) are considered DLT, except for the hematologic DLT for patient with acute leukemia that must be confirmed after 6 weeks of treatment,

#### Treatment compliance

Patients will record daily in a specific diary, the number of capsules swallowed, time of intake, as well as possible reactions, including vomiting, and their time of occurrence. At each study visit the hospital pharmacist of the study center will provide the patient with the needed number of capsules for the visit interval and retrieve the unused capsules that will be kept until study end for accountability by the study monitor.

#### Number of subjects

The total number of patients enrolled will depend on the number of DLs explored and of DLT encountered. Approximately 80 evaluable patients will be enrolled in the dose escalation part (40 by subset AL/OHM) At least 12 evaluable patients by expansion cohorts will be enrolled in at least 3 expansion cohorts

#### Pharmacokinetics (PK)

Blood collection:

Once-a-day schedule

Three patients by DL will have complete PK sampling, consisting of 7 blood draws of 3 mL each at days 1 and 2 (T0, T1h, T4h, T8h, T12h and T24h, plus one sampling ay either T10h or T16h). Complete PK sampling will preferably be performed in patients hospitalized due to medical reasons. All other patients enrolled at this DL will have limited PK sampling, consisting of 5 blood draws on day 1 (T0, T1h, T4h, T6h and T8h). Patients enrolled into the same DL across both dose escalation subsets (AL/OHM) will be considered for the selection of the 3 patients with complete PK sampling.

In addition, all patients will have blood sampling at T0 (just before drug intake) on days 8, 15 and 22.

• Twice-a-day (BID) schedule

All patients will have complete PK consisting of 8 blood draws of 3 mL each on days 1 and 2 (T0, T20min±5min, T1h±10min, T2h15min±10min, T3h15min±10min, T9h±1h, T12h±15min (before drug intake) and T24h (before drug intake)). Patients will be hospitalized for 24 hours for PK sampling.

In addition, all patients will have blood sampling at T0 (just before drug intake) on days 8, 15 and 22.

### Fresh tumor collection:

OTX015/MK-8628 concentration will be measured in tumor cells.

- Patients with AL will have one bone marrow (3 mL) or one blood (7 mL) sample of at day 8.
- Patients with OHM\* (optional): If a tumor is easily accessible to tumor cell collection using noninvasive method (i.e., skin or superficial lymph node deposits), optional tumor core biopsy will be strongly encouraged, with patient's express additional consent at baseline, and on D15 + 7 days.

Assay method: Ultra Performance Liquid Chromatography with tandem Mass Spectrometry detection (UPLC-MS/MS).

Pharmacokinetic/safety correlations: The incidence and severity of AEs will be compared to Cmax, CL and AUC of OTX015/MK-8628.

### Pharmacodynamics (PD)

Potential biomarkers will be explored in tumor cells, including c-MYC and BRD2, 3 and 4.

- Patients with AL will have 2 bone marrow (3 mL each) and blood (15 mL each) samples at screening and at day 8.
- Patients with other hematologic malignancies\* (optional): If a tumor is easily accessible to tumor cell collection using non-invasive method (i.e., skin or superficial lymph node deposits), optional tumor core biopsy will be strongly encouraged, with patient's express additional consent, for intra tumor PK at baseline, and on D15 ± 7 days.

PD/safety correlation: The incidence and severity of AEs will be compared to the most pertinent biomarker(s), if any.

PK/PD correlation: Cmax, CL and AUC of OTX015/MK-8628 will be compared to the most pertinent biomarker(s), if any.

### As far as possible the same cytology/tissue samples will be used for intratumor PK and PD

### **Predictive biomarkers**

• Available archived tumor material (lymphoma) will be collected, as well as fresh tumor material at baseline (leukemic blasts or optional biopsy for other hematologic malignancies) for preliminary detection of predictive factors of OTX015/MK-8628 clinical antitumor activity. The availability of a paraffinembedded block is a pre-requisite for inclusion of patients with lymphoma into the study if no fresh tumor cells/tissue are available.

#### **Study endpoints**

- Primary: the primary endpoint for the determination of the RD will be DLT
- Secondary: treatment-emergent adverse events (TEAEs), PK and PD parameters, laboratory results, tumor response assessment (according to most recently published standard criteria) (see details by disease in the core protocol), tumor-related symptoms, performance status (PS).
- Exploratory: tumor phenotype, karyotype, molecular biology, etc.

#### Safety parameters

Safety will be assessed on every patient having received the study treatment. It will be evaluated on:

- Vital signs (temperature, breath rate, blood pressure and heart rate), physical examination, within 1 week prior to the first study drug administration and then weekly for 3 weeks, and then every 21 days.
- In addition, vital signs will be collected immediately before, then, 1 and 2 hours (around the Tmax) after the first study drug administration on day 1
- ECG will be performed within one week prior to the first study drug administration, immediately before, then, 1 and 2 hours (around Tmax) after study drug administration at days 1.
- Echocardiography, with measurement of LVEF will be performed at baseline and at the end of treatment.
- AEs will be recorded and graded according to the NCI-CTC (v4.03).

#### Laboratory tests

• *Hematology*:

Complete blood cell counts (CBC): platelets, WBC and differential and hemoglobin, INR, will be performed within 7 days prior to the first study drug administration, then at day 1, then weekly during the first 3 weeks and then every 3 weeks thereafter. In cases of grade >2 hematologic toxicity CBC will be performed twice a week until recovery to grade  $\leq 2$ . In case of neutropenia/thrombocytopenia grade 4, CBC will be performed at least every other day until recovery to grade  $\leq 3$ . In addition, in cases of thrombocytopenia grade 4 lasting > 3 days, a bone marrow aspiration is to be performed. In cases of fever  $\geq 38^{\circ}$ C, infection, purpura or bleeding, additional CBC should be done as clinically indicated.

• Biochemistry:

LDL, HDL,  $\beta$ 2-microglobulin (only for patients with myeloma), serum creatinine, glucose, ionogram (sodium, potassium, chloride, HCO3. (bicarbonate)), calcium, phosphorus, magnesium, total protein, albumin, AP, ASAT, ALAT, total bilirubin, LDH, CPK and CRP will be performed within 7 days prior to the first OTX015/MK-8628 intake, then at day 1, then weekly during the first 3 weeks, and then every 3 weeks thereafter. In addition, apolipoprotein A-1 (Apo A1) will be assessed within 7 days prior to first OTX015/MK-8628 intake and at day 22 only.

• Urinalysis:

Dipsticks for protein, glucose and blood at day 1, 2, 8, 15, 22, then every 3 weeks.

#### **Efficacy parameters**

- Tumor response will be evaluated using standard criteria for lymphoma, acute leukemia and multiple myeloma.
- Any hints of anti-tumor activity will be quantified and recorded, even if they do not meet criteria for response
- Overall survival (OS)

#### **Statistical considerations:**

This is an exploratory Phase I study aimed to assess the pharmacological effects of OTX015/MK-8628 in humans with hematologic malignancies. The small subject sample size by cohort does not allow for statistical hypotheses. The decisions will be taken by a board of experts (SMC) and the recommended dose will be validated in further studies.

Study duration and dates	Enrolment: 24-26 months according to the number of DLs explored.
	First-patient in: January 2013
	Last patient in: December 2015- January 2016
	End of study follow-up. December 2010

# 4. ABBREVIATIONS

AE	Adverse Event
AL	Acute Leukemia
ALL	Acute Lymphoblastic Leukemia
AML	Acute Myeloid Leukemia
ALAT	Serum Alanine Aminotransferase
AP	Alkaline Phosphatase
Apo Al	Apolipoprotein A-1
ASAT	Serum Aspartate Aminotransferase
aSCT	Allogenic Stem Cell Transplant
ASCT	Autologous Stem Cell Transplant
BID	Twice Daily
BJ	Bence Jones Protein
BMI	Body Mass Index
BP	Blood Pressure
BRD	Bromodomain
BSA	Body Surface Area
CBC	Complete Blood Count
СНОР	Cyclophosphamide, Adriamycin, Vincristine, Prednisone
CI	Confidence Interval
СРК	Creatine PhosphoKinase
CR	Complete Response
CRi	CR With Incomplete Blast Clearance
CRF	Case Report Form
CRO	Contract Research Organisation
CRP	C-Reactive Protein
CSC	Clinically Significant Change
СҮР	Cytochrome P
DIC	Disseminated Intravascular Coagulation
DL	Dose Level
DLT	Dose Limiting Toxicity
ECG	Electrocardiogram
ECOG	Eastern Cooperative Oncology Group
GCB	Germinal Center B-Cell-Like
GVHD	Graft Versus Host Disease
IMid	Immunomodulatory Drug
INR	International Normalized Ratio
ITT	Intent To Treat

LDH	Lactate Dehydrogenase
LFTs	Liver Function Tests
LVEF	Left Ventricle Ejection Fraction
MDRD	Modification Of Diet In Renal Disease
MLFS	Morphologic Leukemia-Free State
MM	Multiple Myeloma
MTD	Maximum Tolerated Dose
NA	Not Applicable
NCI-CTCAE	National Cancer Institute -Common Toxicity Criteria For Adverse Events
OHM	Other Hematologic Malignancies
PC	Predefined Change
PD	Progressive Disease
РР	Per Protocol
РК	Pharmacokinetics
POEMS	Polyneuropathy, Organomegaly, Endocrinopathy, M-Component, Skin Changes
PR	Partial Remission
PS	Performance Status
РТ	Preferred Term
QD	Daily
RD	Recommended Dose
SAE	Serious Adverse Event
SAP	Statistical Analysis Plan
SD	Stable Disease
SMC	Safety Monitoring Committee
SCO	System Organ Class
TEAE	Treatment Emergent Adverse Event
Tmax	Time To Peak Concentration
UNL	Upper Normal Limit
UPN	Unique Patient Number
WHO	World Health Organization

# 5. STUDY CONDUCT

The study has been completed and the current SAP applies to all the patients included in the study (dose escalation and cohort expansion).

All statistical programs employed in the analysis, data reporting and statistical outputs will be validated by the statistician in charge of the study. In addition, primary criteria (DLT) will be validated by a second eXYSTAT statistician.

# 6. STATISTICAL METHODOLOGY

# 6.1 GENERAL CONSIDERATIONS

The statistical analysis will be performed by eXYSTAT, under the responsibility of the Sponsor OncoEthix GmbH and the study CRO, OTD, on the basis of the present document.

The statistical analysis will be performed using SAS® software, version 9.4 in a Windows XP operating system environment.

The baseline value is defined as the last available value prior to administration of the investigational product.

The study treatment phase is defined as the period between the date of first administration of investigational product and the date of last administration of investigational product + 30 days.

No replacement of missing values is planned, other than those noted in Section 6.2. Thus the number of patients included in the analyses may vary depending on availability of the parameter considered.

Descriptive statistics will be provided by dose level (DL1 to DL5 or DL6 then expansion cohort, depending on the disease cohort) and overall for each of the two patient cohorts (AL and OHM), and by time point when appropriate, according to the nature of the variable.

- For quantitative variables, descriptive statistics will include: number of missing values, number of observed values, minimum, maximum and median or mean and standard deviation.

- For qualitative variables, descriptive statistics will include: number and percentage of missing values, number of observed values, frequencies and percentages (only for the overall column) per modality.

Calculated statistics and percentages will be displayed with one decimal, unless otherwise specified.

No statistical tests will be performed due to the descriptive nature of this analysis.

In terms of terminology, the mention of "by dose level and overall" will always correspond to the following, according to the cohort:

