### Acute Leukemia Patients

		DL3A	DL3B	DL4A	DL4B	DL5A	DL5B	DL6	Exp. (80mg QD) 14-21	Exp. (80mg QD) 14-21	
DL1 (10mg	DL2 (20mg	(40mg QD)	(20mg BID)	(80mg QD)	(40mg BID)	(120mg	(120mg	(160mg	– AML/de	_	
QD) 14-21	QD) 14-21	14-21	21-21	14-21	14-21	QD) 14-21	QD) 21-21	QD) 14-21	novo	AML/MDS	Total
(N=3)	(N=3)	(N=4)	(N=3)	(N=4)	(N=8)	(N=7)	(N=6)	(N=7)	(N=19)	(N=16)	(N=80)

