# **12.3 PRIMARY CRITERION: DOSE LIMITING TOXICITY**

DLTs are defined as any treatment-emergent adverse events (TEAEs) occurring during the first cycle (i.e., the first 21 days following study treatment initiation; note that hypocellular bone marrow and no marrow blasts in AL patients had to be confirmed at day 43), leading to treatment interruption or dose adjustment, or any unforeseen drug-related AE leading to study treatment interruption or discontinuation, unless a relationship to study medication can be definitively ruled out.

The number of patients evaluable for DLT/with DLT in cycle 1 will be tabulated per dose level and overall for safety population.

Type of DLT will be tabulated for patients evaluable for DLT by DL and overall.

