# **12.4 ADVERSE EVENTS**

Adverse events occurring or worsening after the treatment start date and before the last study treatment administration date +30 days were considered treatment-emergent adverse events (TEAEs).

- 21 -

Summary AEs (number and % of patients) will be tabulated by DL and overall for patients with:

- at least one treatment-emergent grade 1-5 adverse event (TEAE)
- at least one related treatment-emergent grade 1-5 adverse event (TEAE)
- at least one treatment-emergent grade 3-5 adverse event (TEAE)
- at least one related treatment-emergent grade 3-5 adverse event (TEAE)
- at least one serious TEAE
- at least one serious TEAE related to the study treatment
- a TEAE leading to treatment discontinuation
- a related TEAE leading to treatment discontinuation
- a TEAE leading to death

Tables of individual TEAEs (number and % of patients) grouped by primary System Organ Class (SOC) and Preferred Term (PT; for MedDRA) will be presented by DL and overall. Patients will be counted only once per primary SOC and PT.

These tables will be presented for all cycles as well as for cycle 1 only.

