# 12.6.3 Individual clinically significant abnormalities

For each hematology and chemistry parameter, number and percentage of patients with at least one clinically significant value (according to the investigator) during the study as well as number and percentage of patients with at least one NCI-CTCAE worst grade of 3 to 5 during the study will be presented by DL.

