### 12.7 VITAL SIGNS, PHYSICAL FINDINGS AND OTHER OBSERVATIONS RELATED TO SAFETY

# 12.7.1 Vital Signs

Raw values and changes from baseline of systolic/diastolic blood pressure (mmHg), Heart rate (beats/min) and respiratory rate (/min) will be described for each visit and for the last value during the study treatment phase by DL.

For weight (kg), systolic/diastolic blood pressure (mmHg) and heart rate (beats/min), number and percentage of patients with at least one predefined change (PC)/clinically significant change (CSC) during the study treatment phase will be presented by DL.

Parameter	Predefined change (from baseline)	Clinically significant change
Weight	Increase $\geq 5\%$	
	Decrease $\geq 5\%$	
Systolic blood pressure	Increase $\geq 20 \text{ mmHg}$	≥180 mmHg and PC Increase
	Decrease $\geq 20 \text{ mmHg}$	$\leq$ 90 mmHg and PC Decrease
Diastolic blood pressure	Increase $\geq 15 \text{ mmHg}$	≥105 mmHg and PC Increase
	Decrease $\geq$ 15 mmHg	$\leq$ 50 mmHg and PC Decrease
Heart rate	Increase $\geq 15$ bpm	≥120 bpm and PC Increase
	Decrease $\geq$ 15 bpm	$\leq$ 50 bpm and PC Decrease

Predefined changes and clinically significant changes are defined below:

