# **16. APPENDIX**

# 16.1 PROPOSED STATISTICAL OUTPUT TABLES

Templates of the planned tables and listings for the Clinical Study Report are provided as presented for two dry runs performed on 18 December 2016 & 11 February 2017 and validated by the Sponsor/Sponsor Representative.

Changes to the data presented or format may be made during the programing on the basis of the output results in agreement with the Sponsor Representative and the Statistician.

Each table will be presented for each of the two patient cohorts - the AL population and Other Hematologic Malignancies population - independently (a single table is shown per analysis with AL header); exceptions are noted when distinct tables are required for the two cohorts (disease characteristics, hematology examinations, efficacy). A representative table for each population is shown. For quantitative variables, % patients will only be reported in the total column, with N patients for individual dose levels.

Tables will be prepared according to the headers in Section 6.1

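### SAP 6.1 and 16.1 confine percentages to a total pooled over all doses and schedules, contradicting 12.4, 12.6.3 and 12.7.1, and no confidence interval or combined AL estimate is planned at the recommended dose

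*SAP*

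**What the plan says.** **The restriction.** SAP 6.1 plans, for qualitative variables, "frequencies and percentages (only for the overall column) per modality". SAP 16.1 repeats this for the table templates: "patients will only be reported in the total column, with N patients for individual dose levels". It introduces that sentence as a rule for quantitative variables, where qualitative must be meant.

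**The contrary instructions.**
- SAP 12.4: "Summary AEs (number and % of patients) will be tabulated by DL and overall". It also plans number and percentage by dose level for the SOC and preferred-term tables.
- SAP 12.6.3, laboratory values: "number and percentage of patients with at least one NCI-CTCAE worst grade of 3 to 5 during the study will be presented by DL".
- SAP 12.7.1: the number and percentage with a predefined or clinically significant change in vital signs "during the study treatment phase will be presented by DL".

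**The primary endpoint.** SAP 12.3: "The number of patients evaluable for DLT/with DLT in cycle 1 will be tabulated per dose level and overall for safety population".

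**The columns.** SAP 6.1 ties the expression for dose level and overall to fixed headers, and 16.1 builds the tables on them. The AL header has two columns labelled "Exp. (80mg QD) 14-21", one for de novo AML and one for AML/MDS, besides escalation level DL4A at the same dose and schedule. The OHM header has one such column, the DLBCL expansion.

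**The purpose of the expansion.** Protocol 3.1.2 and the SAP synopsis say the expansion cohorts are there to confirm, among other things, safety at the recommended dose (RD).

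**Intervals.** The SAP rules out statistical tests. It plans no confidence interval; the term appears only in the abbreviation list.

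**The concern.** Two things are at stake.

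First, a programmer cannot satisfy both sets of instructions. If the general rule in 6.1 and 16.1 prevails, the only percentage printed in each table belongs to a column that mixes every dose and schedule in the cohort. A reader who takes that figure as the toxicity or response rate of the regimen going forward would be misled, by an amount that depends on how strongly the event depends on dose.

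Second, even if dose-level percentages are printed, nothing tells the reader how precisely a rate at the RD is known. In AL the patients on the RD regimen are spread over three columns, so the best-supported estimate the trial can offer is left for the reader to assemble.

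**Working it through.** **1. Check the totals.** Column sizes are from the headers in SAP 6.1.
- AL: 3 + 3 + 4 + 3 + 4 + 8 + 7 + 6 + 7 + 19 + 16 = 80, as stated.
- OHM: 5 + 3 + 4 + 7 + 6 + 7 + 3 + 5 + 5 + 16 = 61, as stated.
- Together 80 + 61 = 141, the enrolled number in SAP 7.

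**2. Count patients on the RD regimen** (80 mg QD, days 1 to 14 of 21, per the SAP synopsis).
- AL: DL4A 4 + expansion 19 + expansion 16 = 39; 39/80 = 48.8%. Expansion alone: 19 + 16 = 35.
- OHM: expansion 16; 16/61 = 26.2%. No OHM escalation column used this regimen: DL4A was 80 mg QD for 21 of 21 days, and the only 14-of-21 escalation column, DL5B, was 120 mg.
- So 41/80 (51.3%) of the AL total and 45/61 (73.8%) of the OHM total come from other doses or schedules.

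**3. How far a pooled percentage can sit from the RD rate.** Pooled = (n at RD × rate at RD + n elsewhere × rate elsewhere) / total. The documents give no event rates, so these are assumptions.

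| Assumed rate at RD / elsewhere | AL pooled | OHM pooled |
|---|---|---|
| 10% / 30% | (3.9 + 12.3)/80 = 20.2% | (1.6 + 13.5)/61 = 24.8% |
| 20% / 20% | 20.0% | 20.0% |
| 30% / 10% | (11.7 + 4.1)/80 = 19.8% | (4.8 + 4.5)/61 = 15.2% |

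With equal rates there is no distortion. Otherwise the pooled figure can err in either direction. In AL it is about 20% in all three rows, although the RD rate runs from 10% to 30%.

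**4. Precision available at the RD.** Exact (Clopper-Pearson) 95% limits: lower = Beta quantile at 0.025 with parameters (x, n − x + 1), upper = Beta quantile at 0.975 with (x + 1, n − x); the lower limit is 0 when x = 0. Event counts are illustrative.

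| Group | n | Upper limit if 0 events | Example |
|---|---|---|---|
| AL DL4A | 4 | 60.2% | 1/4 = 25.0% (0.6 to 80.6) |
| AL expansion, de novo | 19 | 17.6% | 2/19 = 10.5% (1.3 to 33.1) |
| AL expansion, both | 35 | 10.0% | 4/35 = 11.4% (3.2 to 26.7) |
| AL, all at RD regimen | 39 | 9.0% | 4/39 = 10.3% (2.9 to 24.2) |
| OHM expansion | 16 | 20.6% | 2/16 = 12.5% (1.6 to 38.3) |

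Combining the AL columns roughly halves the zero-event upper limit compared with the larger expansion column alone (17.6% to 9.0%). For comparison, the protocol's confirmation limit of one DLT in six gives 16.7% (0.4 to 64.1).

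**5. Denominators.** The 39, 35 and 16 are header counts. SAP 8 defines DLT-evaluable and efficacy-evaluable populations that may be smaller, so these are upper bounds.

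**The case against.** A reader of SAP 6.1 might infer that the only percentages planned are pooled ones, that no output gives a rate at the RD, and that the primary question therefore goes unanswered. The documents do not support this.

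- Dose-level percentages are planned in 12.4, 12.6.3 and 12.7.1. The fault is a contradiction, not an absence.
- SAP 12.3 tabulates DLT-evaluable patients and patients with DLT per dose level, so a crude DLT rate can be read off each column. Response is tabulated per dose level, and the templates have an overall response rate row. The template for the RD determination table shows only its title here, so nothing can be argued from its contents.
- OHM patients on the RD regimen already have their own column. The splitting applies to AL only.
- The range of 10 to 160 mg is that of the AL total; the OHM total stops at 120 mg.
- The primary objective is to select the RD. That is done by a DLT-count rule and the judgement of the Safety Monitoring Committee, and per-level counts serve it.

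All of this stands and limits the point to estimation at the RD. Two further arguments carry less weight. That the study is descriptive rules out tests, but an interval describes precision without testing anything, and small samples make it more useful. That DL4A differs from the expansion, being a dose-selection cohort open to a broader AL population, is a fair caution against relying on the 39 alone. It is met by also showing the 35, and by reporting response by disease.

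**Conclusion.** The point holds as an internal contradiction and an omission. The general display rule conflicts with three specific safety sections. If it is followed, the printed percentages describe a mixture in which fewer than half of AL patients (48.8%) and about a quarter of OHM patients (26.2%) were on the RD regimen. Under the assumed rates of 10% and 30%, the pooled figure misses the RD rate by up to about 15 percentage points. No interval is planned for any endpoint, and the AL data at the RD are never brought together, despite the confirmatory purpose of the expansion.

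This does not undermine how the RD was chosen, and it does not mean that rates at the RD cannot be recovered. The column counts are certain. The size of any distortion is not, because it rests on assumed event rates and on header counts rather than evaluable denominators. The correction should be made, since it uses data already collected.

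**What to change.** 1. In SAP 6.1 delete the bracketed restriction to the overall column, and delete the matching sentence in 16.1 (which also says quantitative for qualitative). Show n and % by dose level throughout, in line with 12.4, 12.6.3 and 12.7.1.
2. Keep the existing columns. Add one AL summary column for 80 mg QD 14-21 (up to N = 39), and show the expansion cohorts alone beside it (up to N = 35).
3. For those AL summaries and the existing OHM expansion column (up to N = 16), give Clopper-Pearson 95% intervals for DLT, grade 3 or higher TEAEs, serious TEAEs, grade 3-4 thrombocytopenia, discontinuation for AE, and response by disease.
4. Use the matching denominator for each: DLT-evaluable, safety, or efficacy-evaluable. For OHM expansion patients, state the DLT-evaluable criterion as 85% of the intended dose, because the 18-day figure given in SAP 8 cannot be met on a 14-day schedule.

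SAP 16.1 already allows agreed changes to the presentation. Since it reports two dry runs, record that these outputs were added after them. The cost is wider tables, one sentence on the interval method, and intervals that will be wide on these sample sizes.
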